12. SUBGROUP ANALYSIS

Subgroup analyses will be performed by forming subsets of patients from the Safety Population, the Primary and Secondary Effectiveness Populations such as:

- Age (≤ 40 , > 40 years). For the Safety Population, enrollment date will be used to determine a patient's age. For the Effectiveness Population, the age will be calculated utilizing Analysis Start Date, ie, diagnosis date for migalastat-treated versus untreated group comparison and start of treatment for migalastat-treated versus ERT-treated comparison.
- Sex (female versus male)
- Renal impairment (Normal [GFR > 90 mL/min/1.73 m 2], Mild [GFR ≥ 60 to 90 mL/min/1.73 m 2], Moderate [GFR ≥ 30 to 60 mL/min/1.73 m 2], Severe [GFR < 30 mL/min/1.73 m 2]). For the Safety Population, enrollment date will be used to determine patient's eGFR. For the Primary and Secondary Effectiveness Populations, the eGFR will be calculated utilizing Analysis Start Date, ie, enrollment date for migalastat-treated versus untreated group comparison and start of treatment for migalastat-treated versus ERT-treated comparison.
- Proteinuria categories based on UPCR (< 0.5 g/g, 0.5 to 1.0 g/g, > 1.0 g/g)
- Classic phenotype in males versus non-classic phenotype (all others: males and females). In males, the classic phenotype of Fabry disease is determined by residual α -Gal A enzyme activity that is minimal or absent (ie, less than 5% of mean normal) and typified by earlier age of onset and more severe symptoms with multiple organ involvement, whereas the non-classic phenotype has residual α -Gal A activity and a later onset, but also is associated with significant disease progression. Use of α -Gal A in the determination of phenotype is applicable to treatment-naïve males only.
- Treatment-naïve ERT-treated versus treatment-naïve migalastat-treated. Treatment-naïve ERT patients are Fabry treatment-naïve patients at the start of ERT. Treatment-naïve migalastat patients are Fabry treatment-naïve patients at the start of migalastat.
- Male patients who have enzyme activity assessment at baseline

For some of the subgroups, only descriptive statistics will be provided due to a small subgroup size.

13. ANALYSIS OF EFFECTIVENESS

13.1. Primary Endpoint

The comparison of interest is between migalastat-treated and untreated patients in the Primary and Secondary Effectiveness Populations. The analysis for the primary effectiveness endpoint will be performed at the 2-sided significance level of 0.05. This analysis will be performed when enough data are available.

Clinical effectiveness will be based on FACEs of cardiac, cerebrovascular, and renal events, and deaths due to FACEs. A composite event is defined as the occurrence of either cardiac, cerebrovascular, or renal clinical event, and death due to FACEs.

Subject matter experts will adjudicate all reports of FACEs. For all summary analyses, the adjudicated decisions will be used if they differ from the initial report. Both original and adjudicated decisions will be reported in listings. Only adjudicated decisions will be used for analyses.

Analyses will be performed in the Primary and Secondary Effectiveness Population.

The analyses described further in Section **Error! Reference source not found.** through Section **Error! Reference source not found.** will be performed for the endpoint of all FACEs combined and separately for all specific FACEs categories listed above (including deaths in these categories) as supportive analyses. A separate analysis of all deaths due to FACEs will also be conducted.

13.1.1. Cox Proportional Analysis for Fabry-associated Clinical Events

The time to the first event is defined as time from the Analysis Start Date to the first composite FACE (primary interest), and to the first cardiac, cerebrovascular, renal clinical event, or death due to FACEs. For the primary analysis, patients who complete the study without an event, are lost to follow-up, discontinued the study, started dialysis, had a kidney or heart transplant, or after 30 days they changed/switched therapy (migalastat group) or after they start therapy (untreated group) will be censored. Describing effectiveness in migalastat treated population is of the main interest.

Treatment Switch

The primary analysis will address events that occur on therapy from the Analysis Start Date up until 30 days after the patient stops therapy or switches therapy. The events that happen afterwards will be excluded. For the patients untreated at time of diagnosis, the primary analysis will address events from the time of diagnosis until the patient starts a therapy. The events that happen afterwards will be excluded. An additional analysis will be performed:

1. An analysis that will address events that occur on therapy from the time of Analysis Start Date up until the patient stops therapy or patient switches therapy. For the untreated patients, the analysis will address assessments from the time of diagnosis until the patient starts a therapy. The events that happen afterwards will be excluded.

Primary Analysis Method

The ratio of the hazards of treatment groups will be checked to ensure that the hazard ratios are constant over time. Secondly, the assumption that each variable in the model makes a linear contribution will be checked.

The covariates will include:

- sex
- age at the Analysis Start Date as a continuous variable
- eGFR_{CKD-EPI} at the Analysis Start Date as a continuous variable
- LVMi at the Analysis Start Date
- previous history of cardiac, cerebrovascular, and renal clinical events (composite event) as related to Analysis Start Date
- Length of treatment for Fabry disease

If the measurements are not available, measurements prior to and closest to the Analysis Start Date will be used. In case that more than 50% of values are missing for a given covariate, it will be dropped from the analysis.

The estimate of hazard ratio for migalastat-treated/untreated along with the associated 95% CI will be calculated.

A sensitivity analyses will be done using Kaplan-Meier approach (log-rank test).

The analysis between migalastat and ERT will be performed like the analysis above for the comparison between migalastat treated and untreated patients. The origination of analysis will be start of treatment.

Because patients could switch treatment many times during the 20-year period, the time to the first event within each treatment period will be calculated from each switch date and descriptive statistics will be presented. Please note that each patient could be counted more than once in this analysis. Two options will be used for these analyses. The first analysis will address events that occur on therapy from the Analysis Start Date up until 30 days after the patient stops therapy or from the switch date to the date of a subsequent switch or stopping therapy. The second analysis will address events that occur on therapy from the Analysis Start Date up until the patient stops therapy or switches therapy or from the switch date to the date of a subsequent switch or stopping therapy.

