## **Endpoints**

### **Primary endpoints**

The primary endpoint is time to first FACE (cardiac, renal, or cerebrovascular events) since each baseline, with particular focus on the added value of the recent addition of Migalastat as a treatment option.

FACEs are defined as the following:

- Cardiac clinical events:
  - Myocardial infarction
  - New symptomatic arrhythmia requiring medication, direct current cardioversion, or interventional procedure (e.g., ablation, pacemaker, or defibrillator implantation)
  - Unstable angina defined by national practice guidelines and accompanied by electrocardiographic changes and non-ST segment elevation myocardial infarction [UA/NSTEMI]) and accompanied by electrocardiographic changes
  - Congestive heart failure requiring hospitalization
  - Any major cardiac medical procedure (e.g., valve replacement, stent-implantation, transplant or persistent atrial fibrillation)
- Cerebrovascular clinical events
  - Stroke (documented by a physician)
  - Transient ischemic attack (documented by a physician)
- Renal clinical events
  - Doubling of serum creatinine level from the start of analysis (2 consecutive values)
  - End-stage renal disease (ESRD) requiring long-term dialysis or transplantation
- Death due to FACEs

All FACEs will be analyzed together as a composite endpoint and separately in each category (cardiac, cerebrovascular, and renal).

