3. STUDY ENDPOINTS

3.1. Primary Effectiveness Analysis

The primary endpoint is time to first FACE (cardiac, renal, or cerebrovascular events) ") since start of treatment for migalastat and or ERT and from time of diagnosis for untreated with particular focus on the added value of the recent addition of migalastat as a treatment option. A formal statistical analysis will be using the initial treatment cohort. Descriptive statistics will be calculated since each start of treatment (after each switch).

FACEs are defined as the following:

- Cardiac clinical events:
 - Myocardial infarction
 - New symptomatic arrhythmia requiring medication, direct current cardioversion, or interventional procedure (e.g., ablation, pacemaker, or defibrillator implantation)
 - Unstable angina defined by national practice guidelines and accompanied by electrocardiographic changes and non-ST segment elevation myocardial infarction [UA/NSTEMI]) and accompanied by electrocardiographic changes
 - Congestive heart failure requiring hospitalization
 - Any major cardiac medical procedure (e.g., valve replacement, stent-implantation, transplant, or persistent atrial fibrillation)
- Cerebrovascular clinical events:
 - Stroke (documented by a physician)
 - Transient ischemic attack (documented by a physician)
- Renal clinical events
 - Doubling of serum creatinine level from the start of analysis (2 consecutive values)
 - End-stage renal disease (ESRD) requiring long-term dialysis or transplantation
- Death due to FACEs

All FACEs will be analyzed together as a composite and separately in each category (cardiac, cerebrovascular, and renal). Death due to FACE will be analyzed under the category in which it occurred (cardiac, cerebrovascular, or renal).

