13.4. Secondary Endpoint: Time to first FACE by Category

Time to the first cardiac, cerebrovascular, and renal clinical event separately by each specific category (including death in these categories) from start of treatment or time of diagnosis will be analysed in the same way as the primary endpoint - composite FACEs (section 13.1).

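### The primary time-to-first-FACE analysis lists dialysis start and kidney or heart transplant as censoring reasons, although qualifying dialysis and transplant are themselves FACEs, and nothing says the event takes precedence

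*SAP*

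**What the plan says.** SAP 13.1.1 defines the outcome of the primary analysis: "The time to the first event is defined as time from the Analysis Start Date to the first composite FACE (primary interest"). The next sentence lists who is censored, and includes patients who "started dialysis, had a kidney or heart transplant, or after 30 days they changed/switched therapy (migalastat group"). In that sentence the condition of being event-free is attached to completing the study and is not repeated for dialysis or transplant.

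SAP 3.1 lists two non-fatal renal FACEs: "Doubling of serum creatinine level from the start of analysis (2 consecutive values") and "End-stage renal disease (ESRD) requiring long-term dialysis or transplantation". Among cardiac FACEs it lists "Any major cardiac medical procedure (e.g., valve replacement, stent-implantation, transplant, or persistent atrial fibrillation"). The protocol uses the same components and says: "All FACEs will be analyzed together as a composite endpoint and separately in each category (cardiac, cerebrovascular, and renal").

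The rule travels. SAP 13.1.1 adds: "The analysis between migalastat and ERT will be performed like the analysis above for the comparison between migalastat treated and untreated patients". SAP 13.4 says that time to first cardiac, cerebrovascular and renal event "will be analysed in the same way as the primary endpoint - composite FACEs (section 13.1").

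**The concern.** A patient who reaches end-stage renal disease and starts long-term dialysis has had a FACE under SAP 3.1 and has met a censoring criterion under SAP 13.1.1. If there was no earlier FACE, the record can carry only one status. Two programmers could both follow 13.1.1 and code this patient differently.

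Under the literal coding, the Cox model and the Kaplan-Meier sensitivity analysis estimate time to a FACE other than dialysis or transplant. That is a different endpoint from the one in the protocol and SAP 3.1, and it is the endpoint tested at the two-sided 0.05 level in SAP 13.1. Patients would leave the risk set at the moment of organ failure, so the censoring would also be informative.

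**Working it through.** The documents give no event count, event rate or power figure on this point, so there is no stated figure to reproduce. The check compares the texts and then uses the SAP's own eGFR formula to see who could be affected.

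**1. Does any other text settle the order?**
- SAP 13.2 and 13.3 drop only the events that follow dialysis or transplant. This suggests that the dialysis or transplant itself counts, but these sections govern prevalence and incidence, not the Cox analysis.
- SAP 13.1.1 uses similar wording about later events for therapy switches and starts, but not for dialysis or transplant.
- SAP 13.1 has experts adjudicate FACE reports. That decides what is a FACE, not whether a FACE overrides censoring.
- SAP 6.2 says only that time-to-event data will be censored.
- SAP 7.3 has programs checked against the plan, which helps only if the plan gives one answer.

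None of these states an order.

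**2. How much of the endpoint is in conflict?** SAP 3.1 lists two non-fatal renal components, and one of them (ESRD) collides with the censoring list. Read literally, renal events reduce to confirmed creatinine doubling plus any renal death before censoring. Among cardiac FACEs the overlap is smaller: transplant is one example within the major-procedure item.

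**3. Would creatinine doubling capture these patients first?** In the CKD-EPI formula of SAP 7.2, the creatinine exponent is -1.209 once creatinine is at or above kappa. At constant age:

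eGFR ratio at doubling = 2^(-1.209) = 0.4326, a fall of 56.7%.

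| Starting eGFR (mL/min/1.73 m²) | eGFR at doubling | With 10 years of ageing |
|---|---|---|
| 60 | 60 × 0.4326 = 26.0 | 24.2 |
| 30 | 30 × 0.4326 = 13.0 | 12.1 |
| 20 | 20 × 0.4326 = 8.7 | 8.1 |

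The last column uses 0.4326 × 0.993^10 = 0.4032.

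The documents give no eGFR at which dialysis starts. Under an assumed value D, a patient whose starting eGFR is below D / 0.4326 reaches dialysis before creatinine has doubled:

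| Assumed D | Start below (constant age) | Start below (10 years of ageing) |
|---|---|---|
| 8 | 8 / 0.4326 = 18.5 | 19.8 |
| 10 | 10 / 0.4326 = 23.1 | 24.8 |
| 15 | 15 / 0.4326 = 34.7 | 37.2 |

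For these patients dialysis, not doubling, would be the first non-fatal renal FACE. They fall mainly in the SAP's Severe category (below 30; SAP 9.2 and 12). The cut-offs are not sharp. Doubling needs two consecutive values, and the protocol's Method section offers workups only every one to two years, so some patients who start higher could also reach dialysis before doubling is confirmed.

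**4. Which way would the hazard ratio move?** Let s be the share of the untreated first-event hazard due to dialysis or transplant. The composite hazard ratio is then s × HR(dialysis/transplant) + (1 − s) × HR(other), while literal censoring leaves HR(other). With an assumed s = 0.10:
- HRs of 0.3 and 0.8: 0.1 × 0.3 + 0.9 × 0.8 = 0.75, against 0.80 after censoring.
- HRs of 1.2 and 0.6: 0.1 × 1.2 + 0.9 × 0.6 = 0.66, against 0.60 after censoring.
- HRs of 0.8 and 0.8: no change.

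The shift can go either way or be zero, and the documents do not say which case applies.

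**The case against.** The strongest reply is that the literal reading is applied selectively. The event-free condition is also missing for patients lost to follow-up or discontinued, yet nobody would censor a patient who had a stroke and was later lost. Some implied condition must be read into the whole list. Once it is, only the case where dialysis or transplant is itself the first FACE remains. The definition of time to first FACE and the wording of SAP 13.2 and 13.3 both point to counting it.

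This narrows the problem but does not remove it, because the remaining case is the one in dispute. Counting events before censorings on tied dates does not fully help either. The FACE is ESRD needing long-term dialysis, whereas the censoring trigger is having started dialysis. If ESRD is dated after the first session, censoring comes first and the event is lost.

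Other parts of the reply stand. The list has a proper use: short-term dialysis is not a FACE, and dialysis or transplant may reasonably stop follow-up for an endpoint of which it is not a component. The eGFR cut-offs are illustrations that concern the first renal event, not the primary composite. SAP 17.1 reports no changes from the protocol, but this is weak support: SAP section 1 cites protocol version 2, whereas the protocol reviewed is marked V1. The argument does not need it, since SAP 3.1 itself defines the composite.

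**Conclusion.** The concern holds. As written, SAP 13.1.1 directs censoring at occurrences that SAP 3.1 and the protocol define as primary events, and no text gives the event precedence. The conflict covers one of the two listed non-fatal renal components and the transplant example in the cardiac list. It extends to the migalastat-ERT and organ-category analyses.

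The effect on results cannot be sized. It depends on how many patients have dialysis or transplant as their first FACE for the endpoint analysed, which is not stated and may be none; patients with an earlier FACE are unaffected. The eGFR cut-offs rest on assumed dialysis thresholds of 8, 10 and 15, and the hazard-ratio examples on assumed inputs throughout. Confidence is high that the rule is wrong as written, but no particular effect on the results is claimed. It should be fixed before the primary analysis is programmed.

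**What to change.** Add to SAP 13.1.1, from which 13.4 inherits it:

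> Dialysis or transplant adjudicated as a FACE for the endpoint analysed is an event on its adjudicated event date and takes precedence over censoring. Dialysis or transplant censors follow-up only when it is not itself an event for that endpoint.

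SAP 13.1 mentions adjudicated decisions but not dates, so adjudication should also fix the event date. SAP 13.2 and 13.3 can keep their rule on later events; at most, state there that the qualifying dialysis or transplant is itself counted.

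The cost is SAP wording plus a check that the dates can be retrieved. The protocol's event form has one dated ESKD entry, no separate date for dialysis start or kidney transplant, and no heart-transplant item. The existing censoring rule and the baseline resets for dialysis and transplant patients in SAP 13.7 and 15.6 already need these dates, so the new sentence adds no data requirement of its own.

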## Abstract

Title	Real World Evidence study of Danish Fabry patients: a > 20-year longitudinal retrospective analysis of prospectively collected data.
Rationale and background	
Fabry is a rare X-linked metabolic lysosomal disorder caused by deficiency in the enzyme <math>\alpha</math>-galactosidase A (<math>\alpha</math>-Gal A) by mutations in the GLA gene, encoding the <math>\alpha</math>-Gal A enzyme, which catalyses glycosphingolipids, namely globotriaosylceramide (Gb3). Reduced or absent <math>\alpha</math>-Gal A activity leads to accumulation of Gb3 in various organs as well as cellular dysfunction and inflammation causing physical symptoms and eventual organ failure. Migalastat, an oral chaperone therapy was approved for Fabry patients in 2016 providing an alternative to infusions with enzyme replacement every 2 weeks. Although the initial trials of Migalastat had some both short and extended outcome treatment comparisons, the overall evidence of clinical efficacy is based on too small numbers considering the heterogeneity of the Fabry patient population as well as the very slow progression of the disease. Though the body of real-world evidence is growing, there is a need for more publications of real-world long-term data on clinical outcomes with a focus on treatment with Migalastat.

Research question and objectives	
Research Question
 
Is the incidence and prevalence of Fabry associated clinical events (FACEs) (cardiac, renal, and cerebrovascular) associated with sex, genotype, phenotype at time of diagnosis, biomarkers, and Fabry specific therapy?
 
Objectives
 
To investigate time to first Fabry associated clinical events (FACE) (cardiac, renal, and cerebrovascular) with particular focus on Migalastat clinical outcomes and treatment outcomes preceding Migalastat therapy.
 
To investigate the incidence and prevalence of FACEs with respect to Fabry specific treatment, Migalastat, ERT or no treatment.
 
To describe FACEs in accordance with different geno- and phenotypic groups.
 
To investigate the incidence and time to a first fatal or non-fatal cardiac, renal, and cerebrovascular clinical event, separated by each category.
 
Primary outcomes
 
Time to first FACE (cardiac, renal, and cerebrovascular) with particular focus on Migalastat on clinical outcomes and treatment outcomes preceding Migalastat therapy.

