## **Rationale and background**

Fabry disease is a rare X-linked lysosomal disorder in lysosomes, resulting in a multisystemic disorder caused by deficiency in the enzyme  $\alpha$ -galactosidase A ( $\alpha$ -Gal A) due to mutations in the GLA gene, encoding the hydrolase  $\alpha$ -Gal A enzyme, which catalyses glycosphingolipids namely globotriaosylceramide (Gb3). Reduced or absent  $\alpha$ -Gal A activity leads to accumulation of Gb3 in the lysosomes of various organs, as well as cellular dysfunction and inflammation causing physical symptoms and eventual organ failure (1,2). Fabry disease as an X-linked disorder with a high penetrance, though not 100% in female heterozygotes, although the disease affects both males and females. With the X-linked nature, Fabry disease is suitable for an efficient, high diagnostic yield cascade screening over at least three generations surrounding an index-patient. The Danish National Fabry Centre has now more than 20 years of experience of cascade screening, which has provided a patient population of 115 male and female patients. The prevalence of Fabry disease in the Danish population is estimated to be 1:58000 (males 1:85000, females 1:44000) (3).

Primarily male patients, with early onset classical phenotypes have none or very low  $\alpha$ -Gal A activity, and they inevitably develop multiorgan failure without treatment (4). Patients with late onset of Fabry disease represent both males and females with higher  $\alpha$ -Gal A activity and variable degrees of organ involvement (5). Fabry disease can cause irreversible damage to multiple organs resulting in Fabry associated clinical events (FACEs) such as renal, cardiac, cerebrovascular events, and death (5).

The primary Fabry specific therapy has historically been enzyme replacement therapy (ERT), and as of 2016 an oral chaperone therapy, Migalastat, has been available, providing an alternative to ERT for patients with amenable mutations by increasing their endogenous  $\alpha$ -Gal A enzyme activity (6–14). However, real-world long-term data from well-characterised cohorts with available detailed clinical consecutive observations with focus on treatment with Migalastat and Fabry associated events has not been fully investigated (12–14).

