### **Method**

Retrospective study of prospectively collected patient data with use of secondary patient data from both paper and electronic patient files. All patients are treatment naïve at time of diagnosis, which is defined as time point for a verified Fabry associated genetic mutation in the GLA gene. A baseline time point is further defined by switch of Fabry specific treatment. Both Migalastat and ERT will be studied retrospectively. Also untreated patients will be studied by assessment of relevant clinical and laboratory variables. The patients have been followed from 01.01.2001 until

31.12.2022. All patients with Fabry disease both receiving specific Fabry medication and untreated patients have been offered assessment yearly or every other year by thorough workup, including targeted examinations of organ function and symptoms known to be associated with Fabry Disease.

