## Study workflow

Fabry patients entered the study at their baseline visit (first visit in the center) from 2001 with last follow-up December 2022. Patient data will be grouped for the whole duration of the defined study period, with individual datapoints registered at the specific date of event/measurement. Ideally the datapoints will be used according to their specific dates but may be aggregated according to availability. Details is further described in the statistical analysis plan.

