2. OVERVIEW OF STUDY DESIGN

This is a retrospective study of prospectively collected patient data with the use of secondary patient data from both paper and electronic patient files. All patients are treatment naïve at time of diagnosis. Both migalastat and ERT will be studied retrospectively. Also untreated patients will be studied by assessment of relevant clinical and laboratory variables. The analysis will originate at the time of diagnosis.

The patients have been followed for more than 20 years from 2001 until December 2023. All identified patients with Fabry disease, whether receiving specific Fabry medication or not, have been offered annual or biannual thorough workups including examinations of Fabry associated organ function and symptoms. The study will be carried out at the Danish National Fabry Centre, Department of Endocrinology, Copenhagen University Hospital.

All patients from the Danish National Fabry Centre will be included. Subgrouping is aimed at depending on available numbers: non-amenable, amenable, classic, non-classic, males, females, treated including type of treatment or untreated.

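### Routine migalastat time can start only in 2016 while untreated and ERT time counts from 2001, and the primary Cox analyses neither adjust for nor restrict calendar period

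*SAP*

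**What the plan says.** **Comparison.** SAP 13.1 states: "The comparison of interest is between migalastat-treated and untreated patients in the Primary and Secondary Effectiveness Populations". SAP 13.1.1 repeats the method for migalastat against ERT, with the clock starting at treatment start.

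**Calendar windows.** The protocol's background says that "as of 2016 an oral chaperone therapy, Migalastat, has been available", and its abstract gives the same year for approval. Follow-up begins on 1 January 2001 (Protocol, Method). The protocol ends it in December 2022 ("from 2001 with last follow-up December 2022", Study workflow); the SAP ends it a year later ("followed for more than 20 years from 2001 until December 2023", section 2). Under SAP 13.1.1, untreated time counts from diagnosis to the start of therapy, with no earliest calendar date.

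**Adjustment.** The SAP 13.1.1 covariates are sex, "age at the Analysis Start Date as a continuous variable", eGFR, LVMi, previous FACE and length of treatment. The protocol's list (Primary endpoints analysis) is age, time since diagnosis and previous FACE. The interval-based model in SAP 13.1.2 adds only time-dependent treatment indicators.

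**Elsewhere.** The log-rank sensitivity analysis, the subgroups (SAP 12), the population definitions (SAP 5.2) and the protocol's limitations section contain no calendar year, period stratum or contemporaneous restriction.

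**The concern.** Much of the comparator experience is historical. It comes from years in which no patient could be on migalastat in routine care, and the model has no means of separating treatment from era.

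The documents give reasons why era might matter. The cohort was assembled by more than 20 years of cascade screening around index patients, so the mix of patients entering may have shifted. The data come from both paper and electronic files, so recording of events may have shifted. General cardiac, renal and stroke care may also have changed over two decades.

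The listed covariates do not stand in for calendar year. Two patients of the same sex, age, eGFR, LVMi and FACE history, one diagnosed in 2002 and one in 2018, look identical to the model. Length of treatment is zero by definition in never-treated patients. At stake is the migalastat/untreated hazard ratio, the study's headline estimate, and the migalastat/ERT hazard ratio, which uses the same method.

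**Working it through.** The plan has no figure of its own to reproduce: the sample of about 115 is a census, and no event rate, power or effect size is stated.

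**Inputs from the documents:** follow-up start 2001; migalastat availability 2016; follow-up end December 2022 (protocol) or December 2023 (SAP).

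**Assumptions, not in the documents:** uniform entry over each group's window, no true drug effect, 50 events per 1000 person-years in 2001, and a constant yearly change in the event rate, ranging from a 2% rise to a 5% fall.

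**1. Years without possible routine migalastat time.** 2001–2015 is 15 years. To end 2022: 15/22 = 68%. To end 2023: 15/23 = 65%.

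**2. Calendar gap between groups.** Window midpoints to end 2022 are (2016 + 2023)/2 = 2019.5 and (2001 + 2023)/2 = 2012.0, a gap of 7.5 years. To end 2023 they are 2020.0 and 2012.5, again 7.5 years.

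**3. Approximate distortion.** If the event rate falls by a proportion g per year, the apparent null HR is roughly (1 − g)^7.5. For example, 0.98^7.5 = 0.86. For a 2% rise, 1.02^7.5 = 1.16.

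**4. Simulation check.** Large-sample Cox model on time since start, 400,000 per group, treatment as the only term. Migalastat starts were uniform from 2016 and comparator starts uniform from 2001. The restricted column counts risk time only from 2016, with delayed entry. Follow-up ends in 2022.

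| Yearly change in event rate | Formula | HR, no calendar handling | HR, risk time from 2016 |
|---|---|---|---|
| rise 2% | 1.16 | 1.15 | 1.02 |
| none | 1.00 | 1.00 | 1.00 |
| fall 1% | 0.93 | 0.93 | 0.99 |
| fall 2% | 0.86 | 0.85 | 0.97 |
| fall 3% | 0.80 | 0.79 | 0.96 |
| fall 5% | 0.68 | 0.66 | 0.92 |

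With the 2023 end date the third column reads 1.15, 1.00, 0.92, 0.86, 0.78, 0.66 and the fourth 1.03, 1.00, 0.99, 0.97, 0.94, 0.93. The choice of end date hardly matters.

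**5. Comparator time given up.** Across these runs, 44% to 53% of comparator person-years fell before 2016.

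The simulation carries no covariates, so it gives no credit for case-mix change that the planned covariates would absorb. A calendar-period term was not simulated.

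**The case against.** **Mitigations.** The plan has more protection than age, sex and eGFR. LVMi and previous FACE measure disease burden at entry. The Primary Effectiveness Population is limited to amenable variants meeting migalastat treatment criteria. Only adjudicated FACEs are analysed, and work-up was offered yearly or every other year at one centre throughout. These points stand and narrow the case-mix and detection routes. They do not close them: adjudication acts only on events that were reported, the Secondary Effectiveness Population takes every variant, and none of these features addresses change in background care.

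**Overlap in time.** A reader might infer that era and migalastat are completely confounded. They are not. Untreated and ERT time also accrues after 2016, and that overlap is what makes a contemporaneous comparison possible.

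**Direction.** A reader might also infer that the plan is tilted towards migalastat. The documents give no event rates by period. Better detection over time would raise recorded rates and push the hazard ratio above 1.

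**The migalastat clock.** SAP 3.1 starts it at treatment; SAP 11.2 starts it at diagnosis for the comparison with untreated patients. Under 11.2, time labelled migalastat could precede 2016. That is a separate problem of pre-treatment time; routine on-drug time still begins in 2016. The documents do not say whether any patient had earlier trial exposure.

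**Small numbers.** About 115 patients, before the amenability restriction and the split by treatment, already face six covariates. This is a good reason not to require another term in the main model.

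**Conclusion.** The omission is confirmed, and as planned the hazard ratios for migalastat against untreated and against ERT partly compare a recent treatment with historical controls. Any secular change would be partly confounded with migalastat and left unadjusted. Whether there was such change, how large and in which direction, cannot be told from the documents. The illustrative range, from about 0.79 for a 3% yearly fall to about 1.15 for a 2% yearly rise, rests on uniform entry, a constant trend and no drug effect.

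Two stronger readings are not supported. One is a larger distortion from a 9-year gap: it pairs short untreated spells (mean date 2012) with migalastat spells running to the end of follow-up (2016 + 7 × 2/3 = 2020.7). One assumption applied to both groups gives 5.0 years (2020.7 − 2015.7, where 2015.7 = 2001 + 22 × 2/3) or 7.5 years; at a 4% yearly fall these give 0.96^5 = 0.82 and 0.96^7.5 = 0.74. The other is an inflated false-positive rate: runs at 60 and 115 patients, with assumed splits, had few events and convergence failures and showed no excess. The concern is bias in the reported hazard ratio. It merits a change to the SAP before analysis but does not invalidate the design.

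**What to change.** 1. **Reconcile SAP 3.1 and 11.2 first**, so that only on-drug time counts as migalastat time.
2. **Add a sensitivity analysis to SAP 13.1.1** (migalastat against untreated and against ERT, composite FACE) **and to 13.1.2.** Suggested wording: *All risk time will be counted only from 1 January 2016. Patients diagnosed or started on treatment earlier enter the risk set on that date (delayed entry), keeping their original time origin. The hazard ratio and 95% CI will be reported beside the main result.*
3. **Optional alternative, if event numbers allow:** a time-dependent calendar-period term (2001–2015, 2016 onward). With no routine migalastat time in the first period it largely duplicates step 2, so it need not be mandatory.
4. **State one follow-up end date** in both documents.

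**Cost.** SAP wording and additional model runs; the protocol's forms already record treatment and event dates. The restricted analysis gives up roughly half the comparator person-years under uniform entry, so its interval will be wider. It keeps only patients who were still event-free and under follow-up in 2016, a selection that should be acknowledged. It also leaves drift within 2016–2022/23: under a 5% yearly fall the null HR is still about 0.92–0.93. It therefore belongs beside the main estimate, not in its place.
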